## 3.2.2 Supportive Medications for risk of nausea and emesis

- Participants with baseline nausea and/ or emesis will be continued on their home medication regimen. If this contains ondansetron (a prohibited medication), then ondansetron will be transitioned to an acceptable alternative such as granisetron.
- Participants who do not have a prescribed anti-emetic regimen at baseline or those whose current anti-emetic regimen is deemed insufficient will be prescribed sufficient supply of oral granisetron (1 mg, PRN) to use until first return visit (at 14 days) in case increased nausea/ emesis occurs while taking Minnelide. An alternative anti-emetic may be prescribed in case of participant allergy, intolerance or preference. Refills will be prescribed as needed at subsequent visits.

#### 3.3 DOSE MODIFICATIONS

Two dose-reductions per participant (see **Table 2** below) will be permitted in response to either hematologic or non-hematologic toxicities for criteria as defined in the sub-sections below.

**Table 2: Minnelide Dose Reduction** 

Minnelide Dose Reductions	Minnelide Dose (Low)	Minnelide Dose (High)
Full-dose	2 mg/ day	2.5 mg/ day
1st occurrence of AE requiring dose reduction	1.5 mg/ day (75%)	2.0 mg/day (80%)
2 nd occurrence of AE requiring dose reduction	1.0 mg /day (50%)	1.5 mg/day (60%)
3 rd occurrence of AE requiring dose reduction	No further Minnelide given	No further Minnelide given

A new cycle of Minnelide should not be started if the participant's laboratory values, clinical status or medical conditions no longer meet initial study eligibility criteria as per the assessments to be completed prior to each cycle (see Study Calendar, Section 3.7) with Minnelide held until these values reach eligibility criteria unless otherwise described below (i.e., Section 3.3.1 to 3.3.4).

If treatment is delayed for > 2 weeks due to any drug-related toxicity, the participant must be 1) dose-reduced (as defined above) or 2) discontinued from treatment with Minnelide capsules and

Version Date: 7/10/2025

followed for safety. Cycles of Minnelide are never skipped. If participants are delayed receiving the next cycle of Minnelide for > 2 weeks due to complications of disease, co-morbid conditions, scheduling problems or any reason other than drug-related toxicity, Minnelide should be continued at previously administered dose when these issues have resolved to meet requirements of study eligibility criteria. In such cases where a new cycle of Minnelide is delayed, the duration of the current cycle lengthens to >28 days. A new cycle does not start until a participant takes the first dose of Minnelide for that next cycle.

As defined below, individual doses of Minnelide may be held in response to lab abnormalities or or clinical issues. If Minnelide treatment must be paused in this way, these missed doses are not administered later. Minnelide treatment for the cycle will still finish on Day 21.

## 3.3.1 Neutropenia and Febrile Neutropenia

Minnelide should be halted and growth factor should be given to all participants experiencing grade  $\geq 3$  neutropenia until ANC exceeds  $1500/\,\mathrm{mm^3}$ . After recovery of ANC, dose reduction (see Section 3.3) to next lowest level of Minnelide is required to continue therapy, except if grade  $\geq 3$  neutropenia occurs within first 1-2 weeks of cycle 1. Transient grade  $\geq 3$  neutropenia has been observed during the first 1-2 weeks of cycle 1 in some participants on prior study of oral Minnelide. In this situation, Minnelide should be held until ANC recovers to Grade 1 or better, but can subsequently be resumed at the previous dose. Any subsequent neutropenia events will require dose reduction as specified in Section 3.3.

Febrile neutropenia should always be treated as a medical emergency; Grade 5 sepsis has been observed in patients receiving Minnelide treatment. Minnelide treatment should be halted immediately and growth factor administered to all participants experiencing febrile neutropenia until ANC exceeds 1500/ mm^3. Pan-cultures should be taken as per standard of care and appropriate empiric antibiotic treatment should be promptly initiated. In addition, Minnelide should be held and no new cycle started until ANC exceeds 1500/ mm^3 AND prescribed antibiotic course has been completed. Upon resumption of Minnelide, dose reduction is required for each episode of febrile neutropenia as per Section 3.3.

#### 3.3.2 Thrombocytopenia

Minnelide should be held for grade 4 platelet count decrease or for grade  $\geq 3$  platelet count decrease that is accompanied by new clinically significant bleeding. The current cycle of Minnelide may be resumed at a decreased dose when platelet count exceeds  $50,000/\,\mathrm{mm^3}$ . Dose reductions should be made as specified in Section 3.3. To start next cycle, platelets must recover to that specified by eligibility criteria and Minnelide should be administered at the decreased dose. Any subsequent grade 4 thrombocytopenia events or grade 3 events associated with clinically significant bleeding will require dose reduction as specified in Table 2.

#### 3.3.3 Anemia

Minnelide should be held for grade  $\geq 3$  anemia. The current cycle may be resumed when Hgb exceeds 8.0 g/dL. Transfusion may be given to increase Hgb. Minnelide should be dose-reduced if participant requires transfusion 2 or more times due to drug-related anemia or if Hgb has not recovered to at least 8.0 g/dL by the scheduled start of the next cycle. Dose reductions should be made as specified in Section 3.3. Any subsequent occurrences of anemia requiring transfusion or failure of Hgb to recover to at least 8.0 g/dL by the scheduled start the next cycle will require further dose reduction as specified in Section 3.3.

Version Date: 7/10/2025

## 3.3.4 Non-hematologic toxicity

Minnelide should be held for any clinically significant grade  $\geq 3$  non-hematologic toxicity. The present cycle of Minnelide may be resumed when toxicity resolves to at least grade 1 (or to baseline in participants with liver metastases and elevated transaminases). If the clinically significant toxicity is attributable to study drug, then Minnelide should be dose-reduced when resumed. If the adverse event is judged to be unrelated or unlikely to be related to Minnelide, then Minnelide may be resumed at the previous dose.

Asymptomatic grade  $\geq 3$  electrolyte abnormalities than can be rapidly corrected with supplementation are not considered clinically significant.

Nausea, vomiting or diarrhea that resolve within 48 hrs of initiating appropriate supportive medications are not considered clinically significant. **NOTE:** See contraindication for concomitant use of ondansetron in Section 4.

## 3.4 ON TREATMENT EVALUATIONS

The following describes all tests and procedures to be conducted during treatment. Refer to Study Calendar (Section 3.7) for timing and applicable windows.

For each time period, consider the following order of assessments:

- Baseline/Cycle 1: The results of all assessments, with the exception of tumor markers, must be available and reviewed prior to initiation of Minnelide administration to ensure results still meet standards defined in eligibility criteria. The cycle should be delayed if these criteria are not met (refer to Dose Modifications, Section 3.3).
- Subsequent Cycles: The results of all assessments, with the exception of tumor markers, must be available and reviewed prior to initiation of Minnelide administration in a new cycle to confirm eligibility for ongoing treatment administration.
- Mid-cycle Cycle 1/Subsequent Cycles: There is no specific order of events for these
  days. The study team must review results of laboratory studies within 2 calendar days of
  the blood draw.
- Unscheduled Visits: In the event of an unscheduled/unplanned visit (e.g., additional clinical assessment(s) due to toxicity), the investigator should use best clinical judgement as to the necessary assessments. In the event that the decision is made to continue treatment, all tests/assessments as required by the next visit on the Study Calendar (Section 3.7) should still be conducted (or repeated) within the applicable windows. If a decision is made to discontinue treatment, the participant should move to the End of Treatment visit (Section 3.5), with tests/assessments completed (or repeated) within the applicable windows.

If a physical exam and vital signs are required by the study calendar, then an in-person clinic visit is required. If only symptom assessment is required, a telehealth visit may be conducted so that participants need not travel to the NIH Clinical Center for evaluation unless preferred by the participant or felt to be clinically indicated by the provider. Given the standard nature of the planned clinical laboratories, interlaboratory variability is not a concern and participants may have clinical labs drawn locally, with results sent to the NIH study team (e.g., via fax); in these cases, an appropriate member of the study team will follow-up remotely to discuss any symptoms and to make recommendations/adjustments, as necessary.

Version Date: 7/10/2025

The following is a description of all procedures:

- Symptom assessment: verbal review of participant's current symptoms
- Physical exam, including vital signs and weight: review of organ systems, weight (kg), and vital signs (i.e., temperature, pulse, respirations, blood pressure). After initiation of study drug, symptom-directed physical examinations will be performed as clinically indicated in the investigator's judgment.
- Performance status (ECOG): an assessment of activities of daily living; see **Appendix A: Performance Status Criteria**
- Clinical laboratories:
  - CBC with differential: includes Neutrophils, Lymphocytes, Monocytes, Eosinophils, Basophils, WBC, RBC, Hemoglobin, Hematocrit, MCV, RDW, Platelet
  - Serum Chemistries: Sodium (NA), Potassium (K), Chloride (CL) Total CO2 (Bicarbonate), Creatinine, Glucose, Urea nitrogen, Alkaline Phosphatase, ALT/GPT, AST/GOT, Total Bilirubin, Direct Bilirubin, Albumin, Calcium, Magnesium, Phosphorus
  - o Urinalysis: protein, specific gravity, glucose, and blood
  - o Pregnancy test: Serum β-HCG for women of child-bearing potential
  - Serum tumor markers: CA19-9 and CEA (or CA-125 if not a secretor of CA19-9 and CEA)
- Imaging scans: CT scans or MRI as required for evaluation (including chest, abdomen, pelvis, and other regions as clinically indicated); may be adjusted to assess additional known sites of disease, as needed. Performed up to 3 days prior to start of every other cycle (typically odd numbered cycles). If radiologic response to treatment is observed (see Section 6.3), confirmatory scans may be performed at 4 week interval (e.g., start of next cycle), and in this case subsequent scans should continue prior to every other cycle thereafter (i.e., prior to even numbered cycles).
- Adverse events and Concomitant medication review: Adverse events (assessed using the NCI CTCAE v5.0) and concomitant medication will be continuously monitored throughout the study until 30 days from last dose of Minnelide or start of new anticancer treatment, whichever comes first. Adverse events that occur beyond 30 days after the last administration will be recorded as noted in Section 6.1.
- Minnelide administration, including dispensing and adherence review: Study drug will be dispensed at each cycle and instructed to be self-administered by participants per schedule-see Section 3.2. Participants will be given a dosing diary (see Appendix B: Participant Medication Diary); to be reviewed at each noted visit for drug adherence/accountability.
- Contraception review: Review of contraception use for men and women of childbearing potential. See Section 2.1.1.9.
- Correlative research samples: Refer to Section 5.
- NIH Advance Directives Form: All participants will be offered the opportunity to complete an NIH advance directives form. This should be done preferably at baseline but can be done at any time during the study as long as the capacity to do so is retained. The completion of the form is strongly recommended, but is not required.

Version Date: 7/10/2025

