#### Arms

Number	Name	Description
1	Minnelide	Treat with Minnelide PO daily, Days 1-21 of each 28 day cycle

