#### 6.3 RESPONSE CRITERIA

For the purposes of this study, participants should be re-evaluated for response every 8 weeks. In addition to a baseline scan, confirmatory scans should also be obtained 4-8 weeks (not less than 4) weeks following initial documentation of objective response.

Response and progression will be evaluated in this study using the new international criteria proposed by the revised Response Evaluation Criteria in Solid Tumors (RECIST) guideline version 1.1 (22). Changes in the largest diameter (unidimensional measurement) of the tumor lesions and the shortest diameter in the case of malignant lymph nodes are used in the RECIST criteria.

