## 6.3.3.3 Evaluation of Best Overall Response

The best overall response is the best response recorded from the start of the treatment until disease progression/recurrence (taking as reference for progressive disease the smallest measurements recorded since the treatment started). The participant's best response assignment will depend on the achievement of both measurement and confirmation criteria.

For Participants with Measurable Disease (i.e., Target Disease)

Target Lesions	Non-Target Lesions	New Lesions	Overall Response	Best Overall Response when Confirmation is Required*
CR	CR	No	CR	≥4 wks. Confirmation**
CR	Non- CR/Non-PD	No	PR	
CR	Not evaluated	No	PR	≥4 wks. Confirmation**
PR	Non- CR/Non- PD/not evaluated	No	PR	
SD	Non- CR/Non- PD/not evaluated	No	SD	Documented at least once ≥4 wks. from baseline**
PD	Any	Yes or No	PD	
Any	PD***	Yes or No	PD	no prior SD, PR or CR
Any	Any	Yes	PD	

Version Date: 7/10/2025

Target	Non-Target	New	Overall	Best Overall Response when
Lesions	Lesions	Lesions	Response	Confirmation is Required*

- \* See RECIST 1.1 manuscript for further details on what is evidence of a new lesion.
- \*\* Only for non-randomized trials with response as primary endpoint.
- \*\*\* In exceptional circumstances, unequivocal progression in non-target lesions may be accepted as disease progression.

Note: Participants with a global deterioration of health status requiring discontinuation of treatment without objective evidence of disease progression at that time should be reported as "symptomatic deterioration." Every effort should be made to document the objective progression even after discontinuation of treatment.

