## 10 STATISTICAL CONSIDERATIONS

### 10.1 OBJECTIVES AND ENDPOINTS

OBJECTIVES	ENDPOINTS	JUSTIFICATION FOR ENDPOINTS
Primary		
To determine the single agent antitumor activity (disease control rate) of the anti-superenhancer agent Minnelide in participants with advanced, previously treated ASCP	Assess disease control rate in the study population, where disease control = best response of CR, PR or at least 16 weeks of stable disease	Establishing disease control in 8 or more of 25 participants with advanced previously treated ASCP would be considered clinically significant.
Secondary		
Determine Minnelide safety in participants with advanced, previously treated ASCP	Identify Adverse Events of grade 2 and above (per CTCAE criteria, version 5.0) related to Minnelide that occur from start of treatment to 30 days after last treatment.	Descriptive endpoint to assess toxicity profile of the study drug in this population.
	Assess rate of Serious Adverse Events related to Minnelide that occur from start of treatment to 30 days after last treatment.	
Assess alternative measures of anti- tumor activity	Determine median time until disease progression, switch to a new systemic treatment or death in the treated population. Data cut-off will occur 1 year after last Minnelide treatment.	Descriptive endpoints that may help to determine sample size needed for future Phase 3 study
	Determine median time until death in the treated population. Data cut-off will occur 1 year after last Minnelide treatment.	
	Determine objective response rate of Minnelide.	

OBJECTIVES	ENDPOINTS	JUSTIFICATION FOR ENDPOINTS
Exploratory		
Identify factors that influence participant response to treatment through detailed molecular analysis of participant tumor, serum and blood cell samples acquired at baseline, on-treatment and at time of progression	For each patient with available samples, we will describe the following properties and consider associations with patient response to therapy:	These endpoints have been selected to help understand why the drug may or may not work, to allow better design of future studies in this patient population.
	Tumor genetic mutations at baseline and at time of progression	Do specific genetic profiles give a patient higher or lower likelihood or response? Does treatment change mutational profile?
	Treatment-related change (between pre-treatment baseline and ~C1D15) in:	

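### After a week-8 response that is not confirmed at week 12, section 3.4 schedules no scan until week 20, so progression seen then leaves 16-week disease control undetermined

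*Combined protocol and SAP*

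**What the plan says.** - **Cycle length** (section 2.4.2, Arms): "Treat with Minnelide PO daily, Days 1-21 of each 28 day cycle".
- **Regular scans** (section 3.4, imaging scans): "Performed up to 3 days prior to start of every other cycle (typically odd numbered cycles". Section 6.3 gives the same spacing: "participants should be re-evaluated for response every 8 weeks".
- **Confirmatory scan.** Section 3.4 is permissive and names one interval: "confirmatory scans may be performed at 4 week interval (e.g., start of next cycle". Section 6.3 is directive and gives a range: "confirmatory scans should also be obtained 4-8 weeks (not less than 4) weeks following initial documentation of objective response".
- **After the 4-week confirmatory scan** (section 3.4): "subsequent scans should continue prior to every other cycle thereafter (i.e., prior to even numbered cycles". The clause applies whatever the confirmatory scan shows.
- **Best response** (section 6.3.3.3): "best response assignment will depend on the achievement of both measurement and confirmation criteria". The accompanying table asks for confirmation of CR and PR at 4 weeks or more.
- **Primary endpoint** (section 10.1): "disease control = best response of CR, PR or at least 16 weeks of stable disease". Sections 10.3 and 10.5.1 instead require stable disease of more than 16 weeks.
- **End of treatment** (section 3.5): imaging is required unless it was done within the previous 4 weeks.

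**The concern.** The move to even-numbered cycles is triggered by an observed response, so the time at which the primary endpoint is assessed depends on outcome. For a confirmed responder this does no harm, because the endpoint is already met. For a participant whose week-8 response is not confirmed, only the stable-disease route is left, and on that path the plan removes the scan at about week 16.

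If such a participant is stable at week 12 and has progressed at week 20, nobody knows whether control lasted 16 weeks. Two scoring conventions are open:

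- Stable disease ends at the last scan without progression. A participant who was truly stable at week 16 is then a failure.
- Stable disease runs to the date progression is documented. A participant who progressed between weeks 12 and 16 is then a success.

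Neither section 6.3 nor section 10 chooses between them, so the choice could be made after the data are seen. The decision rules rest on small counts, 3 of 12 and 8 of 25.

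**Working it through.** **1. The plan's own design figure.** Under a 20% rate, the probability of stopping at stage 1 is P(X ≤ 2 | n = 12, p = 0.20) = 0.0687 + 0.2062 + 0.2835 = 0.558. Section 10.3 states 55.8%, so it is reproduced. The exact type I error of the two-stage rule is 0.099 and its power at 40% is 0.815. The scan issue does not alter the design.

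**2. Scan weeks with no treatment delay.** Cycle k starts at week 4 × (k − 1), and the scan falls 0 to 3 days earlier.

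| Path | Scheduled on-treatment scans, 12 cycles (week) |
|---|---|
| Regular, odd cycles 3 to 11 | 8, 16, 24, 32, 40 |
| Week-8 response plus 4-week scan, 3.4 as written | 8, 12, 20, 28, 36, 44 |
| Same, with the 4-week scan treated as additional | 8, 12, 16, 24, 32, 40 |

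The scan before cycle 5 falls at elapsed day 109 to 112 (15.6 to 16.0 weeks). The scan before cycle 6 falls at day 137 to 140 (19.6 to 20.0 weeks).

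**3. Who is affected.** Only a first response at week 8 matters. After a first response at week 16, an unconfirming but stable scan at week 20 already shows more than 16 weeks without progression. Within the week-8 group:

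| Week 12 | Week 20 | 16-week disease control |
|---|---|---|
| Response confirmed | any | Met through CR or PR |
| Stable | Stable | Met; day 137 to 140 exceeds 112 days |
| Stable | Progression | Undetermined |

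The third row can occur because section 6.3.3.1 measures progression from the smallest sum. As an invented example, take sums of 100 mm at baseline, 70 mm at week 8 and 75 mm at week 12. The response is unconfirmed (25% below baseline) and the week-12 reading is stable. Progression is then reached at 70 × 1.2 = 84 mm.

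**4. How often.** Assumption: exponential progression after week 12 with a median of 8, 12 or 16 weeks, so h = ln 2 / median. The documents give no such figure for this group.

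- Stable at 16, progressed by 20, given stable at 12: exp(−4h) − exp(−8h) = 0.207, 0.164, 0.134.
- Progressed between 12 and 16: 1 − exp(−4h) = 0.293, 0.206, 0.159.

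The first figure is the share wrongly failed under the last-scan convention. The second is the share wrongly credited under the progression-date convention. They are alternatives and should not be added.

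For the number of responders, section 1.2.2.2.1 reports 1 response among 10 assessed on the IV formulation. I assume 1 to 3 of 25, all first seen at week 8 and all stable at week 12 if unconfirmed.

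| Share unconfirmed (assumed) | Wrongly failed | Wrongly credited |
|---|---|---|
| All | 1 × 0.134 to 3 × 0.207 = 0.13 to 0.62 | 1 × 0.159 to 3 × 0.293 = 0.16 to 0.88 |
| Half | 0.07 to 0.31 | 0.08 to 0.44 |

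**5. Effect on power, last-scan convention only.** If the 16-week rate is 40% and progression is exponential, 1 − 0.40^(4/16) = 20.5% of those progression-free at week 16 progress by week 20. Suppose 1 or 2 of 25 (4% or 8%) are otherwise-successful participants on this path and 20% of them lose credit. The effective rate is 0.40 − 0.04 × 0.20 = 0.392 or 0.40 − 0.08 × 0.20 = 0.384. Power falls from 81.5% to 79.4% or 77.1%. Under the progression-date convention no power is lost.

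**The case against.** The endpoint is a duration, and no section requires a scan at week 16. A reader might infer that 16-week stable disease cannot be established on the shifted schedule. The documents do not support that: a stable week-20 scan establishes it, and section 3.5 calls for imaging if treatment stops more than 4 weeks after the last scan.

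A reader might also infer that these participants would be counted as failures. That is one possible scoring rule, and the plan does not state it.

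The 4-week scan is optional in 3.4, and section 6.3 already lets the regular week-16 scan confirm a week-8 response. The shift also keeps the 8-week interval (week 12 to week 20). The effect on PFS is slight, since PFS is descriptive and there is no comparator.

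Nor do other participants keep a clean deciding scan. Without a delay, the scan before cycle 5 at day 109 to 112 never exceeds 16 weeks, so it does not by itself meet the wording in 10.3 and 10.5.1.

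The size estimate is soft. The one IV responder had gastric cancer, and the pancreatic participants listed had stable disease.

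All of this stands and narrows the point. What remains is that a site following 3.4 as written reaches the undetermined case, and neither the scan schedule nor a scoring rule resolves it.

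**Conclusion.** The point holds in a limited form. It concerns participants with a week-8 response, stable disease at a 4-week confirmatory scan, and progression at week 20. Their week-16 status is unknown, and the error can go in either direction depending on a scoring rule that the plan leaves open.

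Well under one participant of 25 is expected to be misclassified: 0.07 to 0.44 if half of 1 to 3 responders are unconfirmed, and below one (at most 0.88) even if all are. These figures rest on assumed response numbers, exponential progression and no cycle delays. A delay would move every scan, because scans are tied to cycle starts.

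One participant is 8.3 points of 12 (1/12) or 4 points of 25 (1/25). A reader might take those as the expected effect. They show only what a single misclassification would do if it occurred.

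Severity is minor. It is worth changing because it touches the primary endpoint and costs almost nothing.

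**What to change.** 1. In section 3.4, replace the clause on later scans. State that a 4-week confirmatory scan is additional and that regular scans continue before odd-numbered cycles for every participant. Add that the regular scan 8 weeks after a first response may serve as the confirmatory scan under 6.3. This also reconciles the permissive 4-week text in 3.4 with the directive 4-to-8-week text in 6.3.
2. For the week-16 scan to decide the endpoint, use one wording in 10.1, 10.3 and 10.5.1 (at least 16 weeks, or more than 16 weeks). State that the scan taken up to 3 days before cycle 5 counts as week 16. Without this, the retained scan would still not satisfy the stricter wording.
3. State how stable-disease duration is measured when scans fall on either side of week 16, since a missed or delayed scan can still produce that case.

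Cost: a few sentences. Over 12 undelayed cycles the number of scheduled on-treatment scans on this path stays at 6. A participant who stops early has at most one more scan.

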#### 3.6 FOLLOW-UP PERIOD

## 3.6.1 30-day Follow-up Visit

The mandatory Safety Follow- up visit should be conducted approximately 30 (+ 5 days) after the last dose of study drug and before initiation of a new anti-cancer treatment, whichever comes first (see assessments, Section 3.7). In addition, the study team will confirm contact information for participant and a designated family member, and remind participant of follow-up contact that will be conducted for survival status.

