## 6 DATA COLLECTION AND EVALUATION

#### 6.1 DATA COLLECTION

The PI will be responsible for overseeing entry of data into a 21 CFR Part 11-compliant data capture system provided by the NCI CCR and ensuring data accuracy, consistency and timeliness. The principal investigator, associate investigators/research nurses and/or a contracted data manager will assist with the data management efforts. Primary and final analyzed data will have identifiers so that research data can be attributed to an individual human subject participant.

All adverse events, including clinically significant abnormal findings on laboratory evaluations, regardless of severity, will be followed until return to baseline or stabilization of event.

Version Date: 7/10/2025

Document AEs from the first study intervention, Study Day 1, through 30 (+5) days following the last dose of study medication, whichever occurs later. Beyond 30 days after the last intervention, only adverse events which are serious and related to the study intervention need to be recorded.

SAE assessment after the 30 days will be documented by a licensed physician listed on the 1572 in the source documents.

All adverse events related to study intervention will be recorded in the study database, regardless of grade. Abnormal grade 1 or grade 2 laboratory values not considered related to study intervention will be recorded in the database as an AE **only** if the laboratory abnormality is characterized by any of the following:

- Results in discontinuation from the study
- Is associated with clinical signs or symptoms
- Requires treatment or any other therapeutic intervention
- Is associated with death or another serious adverse event, including hospitalization.
- Is judged by the Investigator to be of significant clinical impact. AE's related to changes in creatinine, AST, ALT and bilirubin are always considered clinically significant.
- If any abnormal laboratory result is considered clinically significant, the investigator will provide details about the action taken with respect to the test drug and about the participant's outcome.

The PI (or PI designee) evaluation of each AE not captured in the clinical database determining that it meets the criteria above will be documented in the source documents. Note: the investigator performing the assessment must be a licensed clinician listed on the FDA form1572.

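### Section 3.4 stops adverse event monitoring at new anticancer treatment, against Section 6.1 and the Section 10.1 safety endpoints; following 3.4 under-observes participants who switch within 30 days

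*Combined protocol and SAP*

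**What the plan says.** The end of adverse event collection is described in several places.

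- **Section 3.4 (On Treatment Evaluations):** monitoring continues "until 30 days from last dose of Minnelide or start of new anticancer treatment, whichever comes first". It then adds: "Adverse events that occur beyond 30 days after the last administration will be recorded as noted in Section 6.1".
- **Section 3.6.1 (30-day Follow-up Visit):** the safety visit takes place about 30 (+5) days "after the last dose of study drug and before initiation of a new anti-cancer treatment, whichever comes first".
- **Section 6.1 (Data Collection):** events are documented from the first study intervention "through 30 (+5) days following the last dose of study medication, whichever occurs later". After that: "Beyond 30 days after the last intervention, only adverse events which are serious and related to the study intervention need to be recorded".
- **Section 8.2 (Assessment of Safety Events):** for the recording timeframe, the reader is sent to Section 6.1.
- **Section 10.1 (Objectives and Endpoints):** the serious-event endpoint reads "Assess rate of Serious Adverse Events related to Minnelide that occur from start of treatment to 30 days after last treatment". The endpoint for grade 2 and higher events uses the same window.
- **Section 10.5.4 (Safety Analyses):** the fraction of participants with each toxicity is tabulated by grade and type. No rule is given for a shortened observation period.

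**The concern.** The statistical section defines the safety endpoints over a window that the visit-level instructions do not fully collect. Someone working from 3.4 would stop at the start of new treatment, while someone working from 6.1 would carry on to day 30 (+5). Two participants with the same course could then be observed for different lengths of time, depending on which section the staff had open.

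Safety is a secondary objective, and every dosed participant is in the safety evaluation (Sections 10.4 and 10.4.1). Under a crude fraction, a participant whose observation ended early stays in the denominator and counts as event-free for the unobserved days. Who switches early is unlikely to be random, since it depends on why and when Minnelide was stopped. With a safety denominator of 25, for example, one participant whose only related serious event went unrecorded would change that rate by 1/25 = 4 percentage points.

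**Working it through.** The plan gives no figure here to reproduce. The check is a comparison of the texts, followed by an illustration of scale.

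**Step 1: which days are covered.** Take a participant who starts new treatment on day d after the last dose, with d below 30.

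| Period after last dose | 3.4 | 6.1 | 10.1 endpoints |
|---|---|---|---|
| Day 0 to day d | collected | collected | counted |
| Day d to day 30 | not collected | collected | counted |
| After day 30 | refers to 6.1 | serious and related only (all events through the +5 days) | not counted |

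The conflict is confined to the middle row. The cross-reference in 3.4 concerns events after day 30 only, so it does not fill that row. Read literally, a related serious event on day 40 is recorded, while one on day 20 in a participant who switched on day 14 falls outside 3.4. For anyone who does not switch within 30 days, the 3.4 and 10.1 windows coincide.

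**Step 2: is switching before day 30 plausible?** No rate is given, but the documents make it credible.

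- The last dose of a completed cycle is on day 21. Scans may be done up to 3 days before the next cycle, for example on days 26 to 28, which is 26 − 21 = 5 to 28 − 21 = 7 days after the last dose. If progression is found then, 23 to 25 of the 30 days still lie ahead.
- This trial's own washout from prior chemotherapy is 2 weeks (exclusion criterion 2.1.2.4).
- Section 10.1 counts a switch to new systemic treatment as an event in its progression endpoint, so switching is expected.

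**Step 3: follow-up time lost under 3.4.** The share of the 30-day tail covered for one participant is d/30:

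- d = 7: 23%
- d = 14: 47%
- d = 21: 70%
- d = 28: 93%

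For the whole group, mean days lost = f × (30 − d), where f is the share switching. Both f and d below are assumptions. A participant who completes two cycles takes the last dose on day 28 + 21 = 49, so the full endpoint window is 49 + 30 = 79 days.

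| f | d | Mean days lost | Share of 30-day tail | Share of 79-day window |
|---|---|---|---|---|
| 0.2 | 21 | 0.2 × 9 = 1.8 | 6% | 1.8/79 = 2% |
| 0.4 | 15 | 0.4 × 15 = 6.0 | 20% | 6/79 = 8% |
| 0.6 | 10 | 0.6 × 20 = 12.0 | 40% | 12/79 = 15% |

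With more cycles the last column gets smaller.

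**Step 4: from lost days to undercounted participants.** A participant is missed in a crude fraction only if the first qualifying event falls between the switch and day 30. The undercount is therefore f × g, where g is the chance of this in an early switcher. It cannot exceed f, and the documents give neither quantity.

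**The case against.** The strongest reply is that the plan already has a governing rule. Section 6.1 is the data collection section, Section 8.2 sends the recording timeframe there, and its window covers the 10.1 endpoints in full. Section 3.4 is headed as on-treatment evaluations and is the outlier. This stands to the extent that a reader might infer from 3.4 that the endpoint window will be only partly observed. The documents do not support that as a certainty: the gap appears only if 3.4 is followed. The reply does not remove the conflict, because 3.4 is an explicit instruction and nothing ranks the two sections.

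A reader might also take the 6% to 40% in the working as the bias in event rates. It is not. It is a share of the post-dose tail under assumed switching rates. Both endpoints count only events related to Minnelide. Section 1.2.2.2 reports a triptolide half-life below 30 minutes and neutropenia resolving within a couple of days off drug (intravenous study), and no detectable triptolide at 240 minutes (oral study). New related events late in the tail may therefore be few, although they cannot be excluded.

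The serious-event endpoint is the less exposed of the two, since 6.1 asks for related serious events even after day 30. Section 3.6.1 is a rule on visit timing, not a collection window; it matters because the visit can fall before day 30.

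Finally, ending collection at new treatment is a legitimate design, and writing that stop into 10.1 and 6.1 would also restore consistency. That is true. But it would change two sections that already agree, and events not collected cannot be recovered, whereas collected events can be set aside.

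**Conclusion.** The contradiction is real and in the current text: 3.4 stops at new anticancer treatment, while 6.1 and both 10.1 safety endpoints do not. If 3.4 is followed, participants who start new treatment within 30 days of the last dose are under-observed, and related grade 2 or higher events and related serious events are probably undercounted. The direction follows from crude fractions that treat unobserved days as event-free. The size cannot be stated, because no switching rate or timing of related events after the last dose is given.

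The consequence is limited. The safety endpoints are descriptive, with no test or decision rule attached, and the primary endpoint, the two-stage rule and the sample size are untouched. The correction is still worth making, because it is cheap and the missing data could not be restored at analysis.

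**What to change.** 1. **Section 3.4:** reword so that adverse events are collected to 30 (+5) days after the last dose regardless of new anticancer treatment, matching 6.1 and covering the 10.1 window.
2. **Flag:** use the start date of new treatment to mark later events, and show the safety tables with and without them. Section 10.1 already needs this date for systemic treatment because its progression endpoint counts the switch; non-systemic anticancer treatment would need its date recorded as well.
3. **Section 6.1:** delete the closing words about whichever is later. Only one time limit is given, so there is nothing to compare.
4. **Section 3.6.1:** state that day-30 safety information may be obtained remotely if the visit took place earlier because of new treatment. Sections 3.5 and 3.6.2 already accept remote contact, and the study calendar lists no physical examination at the 30-day visit.

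The cost is a wording amendment and at most a few more weeks of event recording for participants who switch early. The downside is that some events after the switch will be harder to attribute to Minnelide; the flag makes this visible but does not remove it.
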